2.5 Coding dictionaries

- Adverse events: IMDRF current version
- Baseline findings: not applicable
- Medical history: not applicable
- Medication: not applicable

3 Statistical Evaluation

3.1 Populations for Analysis

All patients who did not undergo at least one enteroscopy will be considered as dropouts. Dropouts will be excluded from any statistical analyses.

Four different analysis populations will be defined:

The **core safety population (cSAF)** will consist of all patients who underwent at least one enteroscopy. Training patients will not be part of the cSAF.

The **general safety population (SAF)** will consist of all patients who underwent at least one enteroscopy including the training patients.

The **core intent-to-treat population (cITT)** will include all patients who underwent at least one enteroscopy and did not have any major protocol deviations. Training patients will not be part of the cITT.

The **general ITT population (ITT)** will comprise all patients who underwent at least one enteroscopy and did not have any major protocol deviation including the training patients.

Only patients of part A are covered by this SAP. For the analysis of data from patients of part B (ERCP patients), a separate SAP will be prepared.

The safety analysis will be performed on the safety population (SAF), which consists of all patients who underwent at least one enteroscopy.

Efficacy analyses will be based on the intent-to-treat (ITT) population, which includes all patients

- who underwent at least one enteroscopy and
- who had not major protocol deviations.

Note: Final decisions regarding validity will be made during the Review Meeting and documented in the Review Report (see Section 1.3).

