3.6 Efficacy Analysis

The following efficacy analyses will be performed based on the cITT population and on the ITT population as sensitivity analysis:

- The anatomical success rate (number of cases in which the suspected anatomical region is reached compared to all attempts) will be computed alongside with its 95% Clopper-Pearson confidence interval.
- The therapeutic yield (percentage of patients with any endoscopic intervention/therapy with exception of biopsies) will be presented alongside its 95% Clopper-Pearson confidence interval.
- The total procedure time (period in minutes needed to complete the procedure) will be summarized descriptively.
- The total therapeutic intervention time will be summarized descriptively.
- The total small bowel enteroscopy rate (number of complete evaluations of the small bowel divided by all attempts to reach the small bowel) will be computed alongside its 95% Clopper-Pearson confidence intervals.
- The outcomes for the items in the user feedback for the judgement of handling characteristics and other aspects will be tabulated in frequency tables.
- Diagnostic Yield (i.e. diagnosis, that explains findings from previous imaging or establishes a new diagnosis, that could explain clinical symptoms, that indicated PSE)
 - Diagnostic Yield is defined as the difference of proportion of patients for which a diagnosis was made and the proportion of patients with prior positive imaging (VKE, MRI, other)

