11.1.7.5 Procedure with PowerSpiral - Categorical Parameters - SAF and cSAF Reference: annCRF page 16-17 Parameters: Procedure with PowerSpiral, Procedural information Analyses: absolute and relative frequencies	FT
11.1.7.6 Procedure with PowerSpiral - Continuous Parameters - SAF and cSAF Reference: annCRF page 16-17 Parameters: Length of procedure, Time to reach deepest point of enteroscopy, Time score out Analyses: descriptive statistics	DT
11.1.7.7 Therapeutic Interventions - Listing of Comments - SAF and cSAF Reference: annCRF page 17 Parameters: Freetext, Start and Stop time of intervention by patient Analyses: Listing of freetext	GL
11.2.1 Assessment After Procedure - Categorical Parameters - ITT and cITT Reference: annCRF page 18 Parameters: Categorical parameters Analyses: absolute and relative frequencies	FT
11.2.2 Assessment After Procedure - Listing of Comments - ITT and cITT Reference: annCRF page 18 Parameters: Freetext Analyses: Listing of freetext	GL
11.2.3 Evaluation of Procedure - Categorical Parameters - ITT and cITT Reference: annCRF page 19-20 Parameters: Handling, instrument insertion, Precision, time needed, staff and resources needed Analyses: absolute and relative frequencies by category (worse, similar, better)	FT
11.2.4 Evaluation of Procedure - Diagnostic Yield - ITT and cITT Reference: SAP section 3.6 Parameters: positive imaging prior to procedure, information whether a diagnosis was made with PSE Analyses: absolute and relative frequencies	FT

Description of table / figure / listing	Type
11.3.1.1 Adverse Events during procedure - SAF and cSAF Reference: annCRF page 17 Parameters: Trigger question on AEs Analyses: absolute and relative frequencies	FT
11.3.1.2.1 Adverse Events by category - SAF and cSAF Reference: annCRF page 23 Parameters: Adverse event category Analyses: absolute and relative frequencies	FT
11.3.1.2.2 Serious Adverse Events by category - SAF and cSAF Reference: annCRF page 23 Parameters: Adverse event category Analyses: absolute and relative frequencies	FT
11.3.1.3 Adverse Events by category - Listing of other AEs - SAF and cSAF Reference: annCRF page 23 Parameters: Freetext Analyses: Listing of Freetext	GL
11.3.1.4.1 Adverse Events - Relatedness - SAF and cSAF Reference: annCRF page 23 Parameters: Relatedness Analyses: absolute and relative frequencies	FT

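### The cITT and ITT sets both drop major deviators, so three efficacy rates, diagnostic yield and the full user-feedback table have no planned estimate in all treated non-training patients

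*SAP*

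**What the plan says.** SAP 3.1 defines four sets. The two safety sets, SAF and cSAF, hold every patient with at least one enteroscopy, with and without training patients respectively. The cITT set, also without training patients, "will include all patients who underwent at least one enteroscopy and did not have any major protocol deviations". The ITT set "will comprise all patients who underwent at least one enteroscopy and did not have any major protocol deviation including the training patients". The closing paragraph of SAP 3.1 repeats the deviation filter for the efficacy population.

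SAP 3.6 then states: "The following efficacy analyses will be performed based on the cITT population and on the ITT population as sensitivity analysis". It covers the anatomical success rate, therapeutic yield and total small bowel enteroscopy rate, each with a Clopper-Pearson interval. It also covers procedure and intervention times, user feedback and diagnostic yield. Diagnostic yield is a difference: "Diagnostic Yield is defined as the difference of proportion of patients for which a diagnosis was made", less the proportion with positive imaging beforehand.

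The table list in SAP 3.9 follows the same pattern: "11.2.1 Assessment After Procedure - Categorical Parameters - ITT and cITT", "11.2.3 Evaluation of Procedure - Categorical Parameters - ITT and cITT" and "11.2.4 Evaluation of Procedure - Diagnostic Yield - ITT and cITT". It names no separate table for the three rates, so their sets follow from SAP 3.6.

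Protocol section 7 names one kind of major deviation, a breach of the eligibility criteria, and leaves the list open. Classification takes place at the end of the study. SAP 3.1 assigns final validity decisions to a documented Review Meeting.

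**The concern.** Readers take an ITT set to be one from which no treated patient was removed for a deviation. Here both ITT sets remove such patients, and the analysis offered as a sensitivity check has the same filter. Comparing cITT with ITT shows the effect of training patients and says nothing about the effect of dropping deviators.

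At stake is how a registry meant to describe device performance in daily practice reports its main performance figures. Protocol 3.1.3 calls diagnostic yield the main efficacy endpoint, and Protocol 4.3 says that all available data will be analysed. The one named deviation could be related to outcome. The exclusion criteria include bowel obstruction or stenosis and implanted instruments, which could plausibly make a target harder to reach. If exclusion and outcome are linked, the reported rates describe a selected group, and no planned companion estimate shows by how much.

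**Working it through.** **1. Relations between the sets (SAP 3.1).**

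- cITT = cSAF minus major deviators.
- ITT = SAF minus major deviators.
- ITT minus cITT = training patients without a major deviation.

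The step from cITT to ITT therefore returns no excluded patient.

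**2. Which results lack an unfiltered version.**

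- *Only on cITT and ITT:* the three rates with their intervals (SAP 3.6), diagnostic yield (Table 11.2.4), the five-item user feedback (Table 11.2.3) and the post-procedure assessment (Table 11.2.1).
- *Also on cSAF:* length of procedure (Table 11.1.7.6, on SAF and cSAF). The SAE endpoint is planned on cSAF, SAF, ITT and cITT (SAP 3.7.1).
- *Possibly in part on cSAF:* "11.1.7.5 Procedure with PowerSpiral - Categorical Parameters - SAF and cSAF" may show whether an intervention was done and which segment was reached. The annotated CRF is not available, so this cannot be settled.
- *No set named:* SAP 3.5 plans summaries of intervention time, complete and incomplete interventions, and the single handling item.

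**3. The plan's own figure.** Protocol 3.3.6 takes 260 patients less 5% drop-out and states 245 (260 × 0.95 = 247, close to the stated figure). The Clopper-Pearson limits in Table 1 reproduce at n = 245; for example, 10/245 = 4.1% gives 2.0% to 7.4%. Neither figure depends on this point, and no allowance is made for deviators.

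**4. How far a rate could move.** The documents give no success rate and no deviator share, so both are assumed. Take N = 245 patients, S successes and m excluded. If exclusion is unrelated to outcome, the expected shift is nil. The extremes are:

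- only successes excluded: (S − m)/(N − m)
- only failures excluded: S/(N − m)

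For an assumed 184/245 = 75.1% (95% interval 69.2% to 80.4%):

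| Excluded | Lower extreme | Upper extreme |
|---|---|---|
| 5 (2%) | 179/240 = 74.6% | 184/240 = 76.7% |
| 12 (5%) | 172/233 = 73.8% | 184/233 = 79.0% |
| 24 (10%) | 160/221 = 72.4% | 184/221 = 83.3% |

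The first two rows stay inside the full-set interval. Only the upper extreme at 10% leaves it.

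Other assumed base rates with 12 excluded:

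- 147/245 = 60.0%: from 135/233 = 57.9% to 147/233 = 63.1%.
- 220/245 = 89.8%: from 208/233 = 89.3% to 220/233 = 94.4%.

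**5. Diagnostic yield as a difference.** Assume 184 patients diagnosed and 147 with prior positive imaging: (184 − 147)/245 = 15.1 points.

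- 5 excluded: (179 − 147)/240 = 13.3 to (184 − 142)/240 = 17.5 points.
- 12 excluded: (172 − 147)/233 = 10.7 to (184 − 135)/233 = 21.0 points.

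The lower values need every excluded patient to have a diagnosis and no prior positive imaging. The upper values need the reverse.

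**6. Limit of this arithmetic.** N = 245 counts patients. SAP 3.6 puts anatomical success and total enteroscopy over attempts, and total enteroscopy applies only where it was intended. The figures show the order of size and do not predict any one endpoint.

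**The case against.** The case for leaving the plan alone has several parts.

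- *The exclusion is stated openly.* SAP 3.1 gives the filter in each definition, and Table 11.1.2 will report the size of all four sets. The number removed will be visible, and a reader could bound the effect as above. This stands, but a bound is not an estimate, and the label still misleads anyone who sees only the results.
- *Unfiltered data already appear.* A reader might infer that the report will hold no result showing whether removal mattered. The documents do not support that: procedure length and the SAE rate can be compared across filtered and unfiltered sets. If Table 11.1.7.5 includes the intervention item, a percentage close to therapeutic yield will also be there on cSAF. Planned individual listings would let a reader rebuild the rest, but no SAP 3.6 rate, diagnostic yield or full feedback table is planned that way.
- *Few deviators are likely.* The eligibility criteria are broad and the contraindications rest on the investigator's judgement. Nothing in the documents points to 5% or 10%. This stands, and it is why the larger scenarios are illustrations only.
- *Dropping ineligible patients suits an objective of use as intended, and without randomisation there is none for ITT to preserve.* This also stands. Making cSAF the main efficacy set would be a preference.
- *Late classification invites selective exclusion.* A reader might infer this from an open list applied at the end of an open-label study. The documents give only partial ground for it: the Review Meeting is documented, and the timeline lists it before the statistical analysis, both in July 2020.

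**Conclusion.** The point holds in a limited form. The two ITT sets are mislabelled, and the sensitivity analysis cannot show the effect of removing deviators. Three rates, diagnostic yield and the full user-feedback table therefore lack a planned SAP 3.6 estimate in all treated non-training patients.

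The consequence is modest. Protocol 4.1.2 rules out hypothesis tests for efficacy. A reader might infer that the SAE non-inferiority conclusion is affected; it is not, because its primary analysis is on cSAF. A reader might also infer that the efficacy results will favour the device. The documents support no direction: the shift may be nil, up or down, and its size depends on a deviator share they do not give. The definitions and planned sets are certain from the text. The numerical bounds rest wholly on assumed rates, assumed shares and a generic patient-level denominator.

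**What to change.** 1. In SAP 3.1 (the definitions and the closing paragraph) and SAP 3.6, rename cITT and ITT as per-protocol sets, without and with training patients.
2. Add the SAP 3.6 efficacy analyses and Tables 11.2.1, 11.2.3 and 11.2.4 on the existing cSAF as a sensitivity analysis, and on SAF where training patients are included.

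The cost is a wording change and one more run of the same tables on sets already defined. The downside is that a few ineligible patients will appear in the cSAF and SAF versions, which a footnote can state.

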3.2 Interim analyses

No interim analyses planned.

3.3 Subgroup analyses

The following subgroups will be additionally considered in the analysis of the primary endpoint:

- Previous abdominal surgery (yes/no)
- Bowel obstruction (yes/no)
- Crohn disease (yes/no)
- Treatment with Acetylsalicylic acid (80 – 100 mg) during procedure (yes/no)
- Treatment with Anticoagulant during procedure (yes/no)
- Procedure changed as compared to initially planned procedure (yes/no)
- Therapeutic intervention (yes/no)
- Concomitant diseases (Inflammation/Polyp/neoplasia/other)

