1.2 Justification for the Design of the Clinical Investigation

Deep enteroscopy is well established with Balloon assisted enteroscopy procedures, however there is a need for innovative and faster methods, less resource utilization which at the same time provide more comfort for the patients.

Currently available and published data for PowerSpiral was collected by means of Investigator Initiated Trials (Mans et al. 2018; Neuhaus et al. 2016; Beyna et al. 2018; Beyna 2018). With this Olympus sponsored Registry further data about performance and safety for this new medical device will be collected in a larger patient population. Obtained safety data will be compared to data published in respective guidelines or literature.

This study will be performed in parallel to the European market launch of this new medical device. It is a registry study with a CE marked medical device whose application within the intended use will be captured. The registry and does not impose any additional procedure or risk to the patient as we strive to document daily clinical routine. Therefor this study is observational (non-interventional) in nature.

For the same reason inclusion criteria are kept as broad as possible. In summary all patients are eligible where the physician realizes an indication for deep enteroscopy for further diagnostic or therapeutic work up. The exclusion criteria will only affect patients under the age of 18 years and pregnant women. Otherwise clinical judgement of the treating physician is the only relevant and leading reason for exclusion. Of course giving signed informed consent by all study subjects is a prerequisite for participation in this "registry".

For this study approximately 12 European sites will be recruited that offer deep enteroscopy to their patients. This international multi-center setup will give a more representative picture and avoid a single-site bias. Furthermore enrollment will be completed earlier compared to a single center approach.

The prevailing complications of a deep enteroscopy are pancreatitis, perforation, bleeding and adverse events associated with sedation or anesthesia (Aktas et al. 2010; Akarsu et al. 2014; Akerman and Cantero 2009; Arulanandan et al. 2016; He et al. 2013; Moeschler and Mueller 2015). Generally these are independent if the procedure was performed as a diagnostic or therapeutic procedure however the complications rate is usually higher in interventional cases (Rondonotti et al. 2018).

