- Discontinuation of Anticoagulant therapy prior / during the procedure
- Provide information about the planned small-bowel enteroscopy
 - Main indication for the planned small- bowel enteroscopy procedure.
 - Select if a capsule endoscopy, CT/MRT enteroclysm or another imaging technique was performed previously.
 - Describe if there were any positive findings during the previous diagnostic workup (e.g. if a bleeding was detected).
- Describe the initially planned PowerSpiral approach
 - Is a total enteroscopy of the small-bowel planned?
 - Start with antegrade procedure and add a retrograde one if unsuccessful or incomplete *or*
 - Start with retrograde procedure and add an antegrade one if the initial procedure is unsuccessful or incomplete *or*
 - Perform a combined antegrade and retrograde examination during a single session.

At visit V2 and V3 (optional):

- At this visit the PowerSpiral enteroscopy will be performed.
- Enter the date and name of the responsible investigator who performs the enteroscopy.
- Enter the total procedure time (“scope-in, scope-out”) measured from initial enteroscope introduction through the bite block to final enteroscope withdrawal through the bite block (minutes) (for antegrade approach) or crossing the linea dentata of the anus in case of a retrograde approach.
- Provide information about the kind of staff and number persons needed for this enteroscopy.
- Select if an antegrade, retrograde or combined enteroscopy was performed.
- Select if a general anesthesia or sedation is used.
- Select which part of the small-bowel was reached.
- Answer if the findings of the previous imaging examinations were confirmed or not.

Clinical Investigation Plan

CIP Reference No.:2018-GI (OEKG) -01. The **SAMISEN** study - Final Version 02 - Date 23th April 2019

- Answer if there was any therapeutic intervention performed. If yes please specify in the free text section.
- Enter the time needed for any therapeutic intervention. If several slots for therapeutic interventions occurred, please add the time needed for each therapeutic slot and enter the total duration in minutes.
- Answer if any Serious Adverse Events occurred during the enteroscopy procedure.
- Document the final diagnosis after the enteroscopy
- Answer the following questions:
 - Was the therapeutic intervention successful and were all planned therapeutic aim(s) achieved?
 - Was the initial therapeutic management plan modified during the procedure?

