11.1.2 Adverse Device Effect (ADE)

An ADE is an adverse event related to the use of an investigational medical device.

Note:

- This definition includes any adverse event resulting from insufficiencies or inadequacies in the instructions for use, the deployment, the implantation, the installation, the operation, or any malfunction of the investigational medical device.
- This definition includes any event that is a result of a use error or intentional misuse.
- This includes medical devices already on the market that are being evaluated for unintended uses, new populations, new materials or design changes.

Clinical Investigation Plan

CIP Reference No.:2018-GI (OEKG) -01. The **SAMISEN** study - Final Version 02 - Date 23th April 2019

11.1.3 **Serious Adverse Event / Serious Adverse Device Effect (SAE /SADE)**

A SAE/SADE is further specified by the fact that it results or could have resulted in death or severe deterioration of health of a subject, user, or other persons, whether (SADE) or not (SAE) related to the investigational medical device.

The criteria for a Serious Adverse Event (SAE) are the following:

- Led to a death,
- Led to a serious deterioration in health of the subject, that either resulted in:
 - A life-threatening illness or injury, or
 - A permanent impairment of a body structure or a body function, or
 - In-patient or prolonged hospitalization, or
 - In medical or surgical intervention to prevent life threatening illness or injury or permanent impairment to a body structure or a body function,
- Led to fetal distress, fetal death or a congenital abnormality or birth defect.

Note: Planned hospitalization for a pre-existing condition, or a procedure required by the CIP, without serious deterioration in health, is not considered a serious adverse event.

The following points should be taken into account when evaluating the seriousness of an Adverse Event:

- The life-threatening criterion indicates that there was an immediate risk of death at the time of its occurrence. This does not mean that if the adverse event had occurred in a more severe form it would have led to death.
- The following events are not considered to be serious adverse events:
 - An event causing a brief visit to a hospital consultation, an open-door or day hospital.
 - Outpatient treatment in the emergency department although the reason for which this treatment was instituted may be serious.

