2.4 Primary and secondary variables

Primary efficacy variable:

The rate of serious adverse events during and after enteroscopy will constitute the primary endpoint for this study.

Secondary efficacy variables:

- Reaching the anatomical region of interest: The rate of successfully reaching the suspected anatomical target region (either by antegrade or by retrograde route) compared to all attempts represents the endpoint 'anatomical success rate'.
- Therapeutic yield: Defined as the percentage of patients with any endoscopic intervention / therapy with the exception of biopsies. (Sethi et al. 2014; Prachayakul et al. 2013; Sanaka et al. 2012)
- Total procedure time: Period in minutes needed to complete the procedure.
- Total therapeutic intervention time: Period in minutes dedicated to therapeutic intervention(s).
- Total small bowel enteroscopy rate: Defined as complete evaluation of the small bowel either with a single approach or combined anterograde and retrograde approach (if complete small bowel enteroscopy is intended anyway (Committee et al. 2015; Gerson et al. 2015).
- Diagnostic Yield (i.e. diagnosis, that explains findings from previous imaging or establishes a new diagnosis, that could explain clinical symptoms, that indicated PSE)
- User feedback and judgment of handling characteristics and other aspects: User feedback and assessment of handling characteristics and other logistical aspects regarding:
 - Handling of PowerSpiral
 - Instrument insertion of PowerSpiral
 - Precision of positioning during therapy of PowerSpiral
 - Time needed for procedure of PowerSpiral
 - Staff and resource needed for procedure of PowerSpiral
- Serious adverse events (PS product related)
- Adverse events during enteroscopy procedure and adverse events (PS product related)

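### Two SAP 3.3 subgroups for the SAE rate, therapeutic intervention and changed procedure, can be set by the SAE itself, so these descriptive comparisons are open to reverse causation.

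*SAP*

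**What the plan says.** SAP 2.4 defines the endpoint: "The rate of serious adverse events during and after enteroscopy will constitute the primary endpoint for this study". SAP 3.3 then says "The following subgroups will be additionally considered in the analysis of the primary endpoint" and lists eight variables, among them "Procedure changed as compared to initially planned procedure (yes/no") and "Therapeutic intervention (yes/no"). Table 11.3.1.9 reports SAEs by these subgroups in the cSAF as counts and percentages only.

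SAP 3.3 defines neither variable. The nearest definition of intervention is that of therapeutic yield in SAP 2.4: "Defined as the percentage of patients with any endoscopic intervention / therapy with the exception of biopsies". Biopsies are taken out; treatment of a complication is not. SAP 3.4.2 and 3.4.7 contain no derivation rules, and SAP 3.4.3 covers only seriousness and attribution to the device.

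Protocol 3.4.2 has the investigator record at V2 and V3 whether a therapeutic intervention was done, with free text, and whether the therapeutic management plan was modified during the procedure. The intended route is recorded earlier, at V1: "Describe the initially planned PowerSpiral approach". Protocol 4.2 plans no subgroup analyses, so these splits rest on the SAP alone.

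**The concern.** A subgroup variable should be fixed before the outcome can influence it. These two are not. A bleed caused by the endoscope in a diagnostic patient and treated through the endoscope makes that patient an intervention case. An SAE that ends a session before the planned therapy has begun leaves the patient recorded without an intervention. An SAE that interrupts a planned combined or total examination may register as a departure from plan. In each case the patient's group follows from the event being counted.

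The intervention split will be read with an expectation in mind, because Protocol 1.2 says that "the complications rate is usually higher in interventional cases". A difference in table 11.3.1.9 could be taken as confirming this, or a lack of difference as refuting it, when misplacement of a few SAE patients explains either. Nothing in the planned table would alert the reader.

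**Working it through.** **Timing.** The endpoint covers events during and after enteroscopy (SAP 2.4). Both grouping variables are recorded at V2/V3 (Protocol 3.4.2). The windows overlap, and no rule in SAP 3.3 or 3.4 orders event and group.

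**How few events are involved.** The plan gives no figure for this point. Its nearest figure is Protocol Table 1, and the exact Clopper-Pearson limits there reproduce: 10/245 gives 4.1% (2.0% to 7.4%). The 8% rule is met with at most 11/245 (upper limit 7.9%; 12/245 gives 8.4%). A study that meets its criterion therefore has about ten SAE patients to spread over each split.

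**Illustration 1: rescue therapy.** All inputs are assumed: 130 diagnostic and 130 therapeutic patients, 6 SAE patients in each group, one SAE per patient, true ratio 1.0. Let k diagnostic SAE patients be treated endoscopically and so be recorded as 'yes'. The rates become (6 + k)/(130 + k) for 'yes' and (6 − k)/(130 − k) for 'no'.

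| k | 'yes' | 'no' | ratio yes/no |
|---|---|---|---|
| 0 | 6/130 = 4.6% | 6/130 = 4.6% | 1.0 |
| 1 | 7/131 = 5.3% | 5/129 = 3.9% | 1.4 |
| 2 | 8/132 = 6.1% | 4/128 = 3.1% | 1.9 |
| 3 | 9/133 = 6.8% | 3/127 = 2.4% | 2.9 |

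The total is 12/260 = 4.6% in every row, so only the split moves.

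**Illustration 2: aborted therapy.** With the same inputs, let k therapeutic SAE patients have their therapy stopped by the SAE and be recorded as 'no'. The columns change places and the ratios invert: 1/1.38 = 0.73, 1/1.94 = 0.52 and 1/2.86 = 0.35 for k = 1, 2, 3. Both mechanisms may act together, so the net direction cannot be stated beforehand.

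**Sensitivity to prevalence.** Take N = 245 and S = 10 SAE patients with no true association. Let π be the share of patients who would be 'yes' anyway, and q the share of otherwise 'no' SAE patients moved to 'yes'. Then:

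- SAE patients in 'yes' = S[π + q(1 − π)]
- all patients in 'yes' = πN + q(1 − π)S

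For π = 0.3 and q = 0.25 this gives 4.75/75.25 = 6.3% against 5.25/169.75 = 3.1%, ratio 2.0. Over q = 0.10, 0.25 and 0.50 the ratios are:

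- π = 0.1: 2.0, 3.9, 9.1
- π = 0.3: 1.35, 2.0, 4.1
- π = 0.5: 1.2, 1.6, 2.9

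The rarer the 'yes' group, the larger the distortion; this would apply to changed procedures if they are uncommon. In the reverse direction, with π from 0.3 to 0.7 and q of 0.25 or 0.50, the ratio runs from 0.69 down to 0.25. The documents give neither π nor q.

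**The case against.** Several counter-arguments have force.

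- **Stakes.** The table is descriptive, with no test and no decision attached. With about ten SAEs, readers will look at the individual cases, and table 11.1.7.7 lists intervention free text with start and stop times. This stands and limits the importance of the point. It does not remove it, because table 11.3.1.9 itself would still carry the misplaced patients.
- **Link through the SAE definition.** Protocol 11.1.3 includes events that resulted "In medical or surgical intervention to prevent life threatening illness or injury or permanent impairment to a body structure or a body function". A reader might infer that every such SAE becomes a therapeutic case. The documents do not support that. The therapeutic variable, as nearest defined, is endoscopic; surgery for a perforation or medical care for pancreatitis would not meet it. Only complications treated through the endoscope move a patient.
- **Meaning of a changed procedure.** The SAP does not define it. Two of the V1 options make the second approach conditional on the first being unsuccessful or incomplete, and V3 is optional. Dropping such a second approach is not clearly a change. The mechanism is plausible for a planned combined session or total enteroscopy, and not general beyond that.
- **Late events.** An SAE arising after a finished procedure cannot have caused an intervention in it, although it may alter a planned second one. The comparisons are therefore open to reverse causation and not circular for every patient.
- **Historical comparison.** A reader might infer that the diagnostic/therapeutic split is decisive for the comparison with balloon enteroscopy. The documents use a single overall limit of 8% and give no historical rate by procedure type, so that inference has no basis.

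**Conclusion.** The point holds as a moderate one. Following SAP 3.3 exactly can place patients in a subgroup because of the SAE being counted, and nothing in the SAP prevents it. Illustration 1 puts the effect at an apparent ratio of 1.4 to 2.9 with one to three rescued patients. Group sizes, event counts and the number rescued are all assumptions, and 2.9 needs half of the diagnostic SAEs to be treated endoscopically.

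Two stronger readings should be resisted. One is that the table would necessarily make diagnostic procedures look safer; aborted therapies push the other way, so the direction for therapeutic intervention is unknown. The other is that the primary conclusion is compromised; regrouping leaves the overall cSAF rate, its confidence interval and the comparison with 8% unchanged.

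**What to change.** In SAP 3.3:

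1. State that endoscopic treatment of a procedural complication does not count as therapeutic intervention. Classify the SAE patients at the review meeting already foreseen in SAP 3.1, using the intervention free text, its start and stop times, and the SAE narratives.
2. Flag SAE patients whose planned therapy was aborted, and show the split with them in either group. The first rule alone does not deal with these patients. V1 has no explicit planned-therapy item, so identification would rest on the indication, prior findings and the V2/V3 answers about therapeutic aims and changes of plan.
3. Split by the approach planned at V1 instead of, or alongside, changed procedure. Alternatively, keep changed procedure but define it and leave out any change caused by the SAE.

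This needs a few lines of SAP text and uses items already collected. It has two drawbacks. Protocol 11.2.1 specifies start and stop dates for adverse events, not clock times, so the order of events within a session is a case-level judgement for a handful of patients; the rule should be written before those cases are reviewed. And a split by planned approach answers a somewhat different question from a split by changed procedure.
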